12.2.3 Reporting adverse events to the responsible IRB

In accordance with applicable policies of the University of Pittsburgh Institutional Review Board (IRB), the Investigator will report, to the IRB, any observed or volunteered adverse event that is determined to be 1) associated with the investigational drug or study treatment(s); 2) serious; and 3) unexpected. Adverse event reports will be submitted to the IRB in accordance with the respective IRB procedures.

Applicable adverse events will be reported to the IRB as soon as possible and, in no event, later than 10 calendar days following the investigator's receipt of the respective information. Adverse events which are 1) associated with the investigational drug or study treatment(s); 2) fatal or life-threatening; and 3) unexpected will be reported to the IRB within 24 hours of the Sponsor-Investigator's receipt of the respective information. Follow-up information to a reported adverse event will be submitted to the IRB as soon as the relevant information is available. If the results of the Investigator's follow-up investigation show that an adverse event that was initially determined to not require reporting to the IRB does, in fact, meet the requirements for reporting; the Investigator will report the adverse event to the IRB as soon as possible, but in no event later than 10 calendar days, after the determination was made.

REFERENCES

APPENDIX I - Schedule of events

	Pre-Treatment	During Treatment	Follow-Up
Histo/cyto eval	X		
History/physical	X		X
Imaging of sites of disease (FDG-PET/CT)	X*		X
Performance status	X	X	X
CBC w/ diff & ANC	X		
Serum pregnancy test (if applicable)	X		
Informed consent	X		
Tumor response eval			X
Adverse event eval		X	X
QOL surveys	X		X

* If one was done within the past 8 weeks, then do not repeat.

APPENDIX II - Performance status scoring

ZUBROD PERFORMANCE SCALE

0	Fully active, able to carry on all predisease activities without restriction
1	Restricted in physically strenuous activity but ambulatory and able to carry work of a light or sedentary nature. For example, light housework, office work
2	Ambulatory and capable of all self-care but unable to carry out any work activities. Up and about more than 50% of waking hours
3	Capable of only limited self-care, confined to bed or chair 50% or more of waking hours
4	Completely disabled. Cannot carry on self-care. Totally confined to bed
5	Death

KARNOFSKY PERFORMANCE SCALE

100	Normal; no complaints; no evidence of disease
90	Able to carry on normal activity; minor signs or symptoms of disease
80	Normal activity with effort; some sign or symptoms of disease
70	Cares for self; unable to carry on normal activity or do active work
60	Requires occasional assistance, but is able to care for most personal needs
50	Requires considerable assistance and frequent medical care
40	Disabled; requires special care and assistance
30	Severely disabled; hospitalization is indicated, although death not imminent
20	Very sick; hospitalization necessary; active support treatment is necessary
10	Moribund; fatal processes progressing rapidly
0	Dead

APPENDIX III - Guidelines for SRS/SBRT dosing and fractionation

Guidelines for SRS (see also section 6.2)

CNS

Treatment will be performed with single fraction SRS/SBRT. Patient will be positioned in supine position with appropriate fixation device, frameless SRS/SBRT can be performed if set-up uncertainty is minimal. SRS/SBRT doses are dependent on lesion size as follows:

Lesion Diameter (cm)	SRS/SBRT dose (Gy)
< 2	24/ 1 fx
2-3	18/ 1 fx
> 3	15 / 1 fx
> 4	30 / 3 fx

For larger lesions, fractionated SRS/SBRT may be used (3 fractions of 10 Gray per fraction) instead of a single fraction of 15 Gy.

LUNG

SBRT to lung lesions will consist of 3-5 treatments depending on location of tumor. Patient will be positioned in supine position with gated treatments or tumor tracking with fiducial markers. For central tumors (defined as within 2 cm of carina, right and left main bronchi, right and left upper lobe bronchi, intermedius bronchus, right middle lobe bronchus, lingular bronchus, and left lower lobe bronchus) SRS dose will be 48 Gy in 4 fractions. For non-central lesions, SBRT dose will be 60 Gy in 3 fractions.

Dose constraints for 48 Gy in 4 fractions:

Organ	Volume	Volume Max	Max Point Dose
Spinal Cord	<0.25 cc	22.5 Gy (4.5 Gy/fx)	30 Gy (6 Gy/fx)
Skin	<10 cc	30 Gy (6 Gy/fx)	32 Gy (6.4 Gy/fx)
Lung (both right and left lung volumes)	1500 cc	12.5 Gy (2.5 Gy/fx)	
Skin	< 10 cc	33.2 Gy (8.3 Gy/fx)	36 Gy (9 Gy/fx)
Chest wall	Any point	32 Gy (8 Gy/fx)	40 Gy (10 Gy/fx)

Dose constraints for 60 Gy in 3 fractions:

Organ	Volume	Max Point Dose
Spinal Cord	Any point	18 Gy (6 Gy per fx)
Esophagus	Any point	27 Gy (9 Gy per fx)
Heart/Pericardium	Any point	30 Gy (10 Gy per fx)
Bronchus	Any point	30 Gy (10 Gy per fx)
Skin	Any point	24 Gy (8 Gy per fx)
Chest wall	Any point	24 Gy (8 Gy per fx)

ADDRENAL

SBRT dose will be 50 Gy in 5 fractions. Patient will be positioned in supine position with gated treatments or tumor tracking with fiducial markers.

Dose constraints

Normal Tissue Constraints	
Organ	Maximum Dose in 5 Fractions
Contralateral Kidney (2/3 volume)	5 Gy
35% of Total (left & right) Kidney Volume	25 Gy
Spinal Cord	20 Gy
Stomach	35 Gy

BONE

Dose and fractionation dependent on size and location. For lesions in vertebral bodies near the spinal cord, single fraction with doses 18-25 Gy. If fractionation is necessary (as deemed by the treating physician, 24 Gy in 3 fractions may be used (8 Gy/fraction). Bone metastatic lesions will not have received previous radiotherapy (see 3.0 for eligibility criteria)

LIVER

Liver lesions less than 6 cm in diameter will be treated to 60 Gy in 3 fractions or 60 Gy in 4 fractions at the discretion of treating physicians. Preference should be given for 60 Gy in 4 fractions, but the shorter course radiotherapy be used to allow for all SBRT treatments to occur within the 3 week time frame. Patient will be positioned in supine position with gated treatments and/or near real-time tumor tracking with fiducial markers.

Dose constraints for liver lesions:

typical estimate of normal liver size is 2000 cm³. At least one-third of the liver should be spared from receiving a dose likely to cause notable hepatic dysfunction, meaning that 700 cm³ should receive a total SBRT dose of less than 15 Gy over 3 fractions and 25 Gy over 5 fractions.

Two-thirds of the right kidney cannot receive a dose of more than 15 Gy in 3 fractions or 25 Gy in 5 fractions.

The percent of total kidney volume receiving a dose of 15 Gy in 3 fractions or 25 Gy in 5 fractions must be less than 35% of the total kidney volume

The maximum dose to any point within the spinal cord can not exceed 18 Gy total in 3 fractions or 20 Gy total in 5 fractions.

The maximum point dose to the stomach can not exceed 30 Gy in 3 fractions or 35 Gy in 5 fractions.

Normal Tissue Constraints		
Organ	Maximum Dose in 3 Fractions	Maximum Dose in 4 Fractions
Liver (700 cm ³)	15 Gy	25 Gy
Right Kidney (2/3 volume)	15 Gy	25 Gy
35% of Total (left & right) Kidney Volume	15 Gy	25 Gy
Spinal Cord	18 Gy	20 Gy
Stomach	30 Gy	35 Gy

LYMPH NODES

Lymph nodes that are considered M1 for primary tumor site will be treated based on size and location. SBRT can range from single fraction 18-24 Gy or 3 fractions to 60 Gy, or 5 fractions to 50 Gy.

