3.2.3 Other

- Lung cancer with pleural effusion (wet IIIB) are not eligible
- Recurrent cancers are not eligible
- Diffuse metastatic spread confined to one organ system is ineligible; examples of this include leptomeningeal spread in the CNS and peritoneal carcinomatosis.

- 3.2.4 Prior systemic chemotherapy for the study cancer; note that prior chemotherapy for a different cancer is allowable but cannot have any other primary cancer diagnosed or treated within the last 3 years other than cutaneous skin cancers. Patient may have previous chemotherapy as treatment of this previous malignancy as long as the chemotherapy has completed more than 3 years ago.
- 3.2.5 Prior radiotherapy to the region of the study cancer that would result in overlap of radiation therapy fields
- 3.2.6 Severe, active co-morbidity, defined as follows:
 - 3.2.6.1 Unstable angina and/or congestive heart failure requiring hospitalization within the last 6 months;
 - 3.2.6.2 Transmural myocardial infarction within the last 6 months;
 - 3.2.6.3 Acute bacterial or fungal infection requiring intravenous antibiotics at the time of registration;
 - 3.2.6.4 Hepatic insufficiency resulting in clinical jaundice and/or coagulation defects; note, however, that laboratory tests for liver function and coagulation parameters are not required for entry into this protocol.
- 3.2.7 Pregnancy or women of childbearing potential and men who are sexually active and not willing/able to use medically acceptable forms of contraception; this exclusion is necessary because the treatment involved in this study may be significantly teratogenic.
- 3.2.8 **Oligometastatic disease sites not eligible based on concern for toxicity:**
 - * trachea involvement (direct invasion, tumors close to or abutting trachea are eligible)
 - * heart (direct invasion or involvement, pericardial lymph nodes can be treated)
- 3.2.9 Patients unable to have an FDG-PET/CT scan, either through insurance coverage, patient decision or other reason are not eligible for this study.
- 3.2.10 Patients unable to have SRS/SBRT through insurance coverage or ability to pay for SRS/SBRT

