6.2.5 Treatment Planning/Target

Gross target volume (GTV) will be the tumor lesion defined by CT scan, FDG-PET scan and clinical information. Planning treatment volume (PTV) will be GTV with margin appropriate for set-up error and movement. There will be no elective nodal coverage.

6.2.6 Radiation doses and fractionation:

Dose and fractionation will be dependent on the lesion location and lesion size, the exact fractionation and dose is at the discretion of the treating physician. However, encouragement is made to adhere to the guidelines outlined in Appendix III. A minimum of 48 hours must be used in between SRS/SBRT treatments at each site. Note that patients can have SRS/SBRT everyday or multiple SRS/SBRT sessions in one day as long as the minimum time for each treatment site is met.

For example, if two lung lesions, adrenal, and liver sites were being treated, both lung sites could be treated Monday, Wednesday, and Friday, the liver on Tuesday, Thursday and the following Tuesday, and the adrenal on Monday, Wednesday, Friday of the second week.

EXAMPLE:

	Mon	Tues	Weds	Thurs	Fri
Wk 1	Lung #1 Lung #2	Liver	Lung #1 Lung #2	Liver	Lung #1 Lung #2
Wk 2	Adrenal	Liver	Adrenal		Adrenal

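### Appendix III's definition of a central lung tumour leaves out the right lower lobe bronchus and the trachea, so some lung lesions near an airway default to the non-central regimen

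*Combined protocol and SAP*

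**What the plan says.** The lung part of Appendix III splits lesions into two classes by distance from named airways. The definition begins "For central tumors (defined as within 2 cm of carina, right and left main bronchi, right and left upper lobe bronchi, intermedius bronchus" and ends "right middle lobe bronchus, lingular bronchus, and left lower lobe bronchus) SRS dose will be 48 Gy in 4 fractions". Everything else falls under one sentence: "For non-central lesions, SBRT dose will be 60 Gy in 3 fractions". No other section defines a central tumour.

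Section 3.2.8, under the heading "Oligometastatic disease sites not eligible based on concern for toxicity", lists "trachea involvement (direct invasion, tumors close to or abutting trachea are eligible". Direct invasion of the trachea is therefore excluded, while a tumour next to it is admitted.

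Section 6.2.6 sets how binding the appendix is. It states that "the exact fractionation and dose is at the discretion of the treating physician" and then that "encouragement is made to adhere to the guidelines outlined in Appendix III".

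The constraint table for 60 Gy in 3 fractions has one airway row: "Bronchus Any point 30 Gy (10 Gy per fx". The table for 48 Gy in 4 fractions, as printed, has rows for spinal cord, skin, lung and chest wall only. M1 lymph nodes have their own guidance in Appendix III, which goes by size and location and offers several regimens.

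**The concern.** The definition sorts lung lesions by closeness to the airways, and the class sets the suggested regimen. Two omissions leave some lesions close to an airway in the class meant for lesions away from the airways.

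The first is one of side: the left lower lobe bronchus is listed and the right is not. The second is a mismatch between sections: 3.2.8 treats tracheal invasion as a toxicity concern and expressly lets in tumours abutting the trachea, but Appendix III gives the trachea no place in the definition and no row in either lung table.

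The primary objective is safe delivery to multiple sites with acceptable toxicity, and toxicity grade is a primary endpoint (sections 2.0 and 11.0). If the suggested dose near an airway depends on an unexplained gap in a list, patient safety is touched directly, and toxicity in such patients is harder to interpret.

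**Working it through.** The plan states no figure on this point to reproduce. The check compares the passages and divides each total dose by its number of fractions.

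**1. Which airways are missing.** Listed: carina, right and left main bronchi, right and left upper lobe bronchi, intermedius, right middle lobe, lingular, left lower lobe. Compared with the right and left upper lobe, right middle lobe, lingular, and right and left lower lobe bronchi, plus the trachea, two are absent: the right lower lobe bronchus and the trachea.

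**2. The regimens on either side of the definition** (Appendix III, lung):
- central: 48 Gy / 4 = 12 Gy per fraction
- non-central: 60 Gy / 3 = 20 Gy per fraction

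**3. Default class, reading the definition literally:**
- within 2 cm of the left lower lobe bronchus: central
- within 2 cm of the right lower lobe bronchus and also within 2 cm of the intermedius, the right middle lobe bronchus or another listed airway: central
- within 2 cm of the right lower lobe bronchus and more than 2 cm from every listed airway: non-central
- lung lesion abutting the trachea and within 2 cm of the carina or another listed airway: central
- lung lesion abutting the trachea and more than 2 cm from the carina and every other listed airway: non-central
- M1 lymph node near the trachea: outside this rule, under the lymph node guidance

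The third and fifth cases are the gap.

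**4. What the constraint tables add.** In the third case the 3-fraction table limits the bronchus to 30 Gy at any point. In the fifth case neither lung table names the trachea.

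**5. Size of the contrast, under an assumption.** The documents give no alpha/beta ratio, so a range is shown. With the linear-quadratic form BED = D × (1 + d / (α/β)), the two prescriptions compare as follows:
- α/β = 2: 60 × (1 + 20/2) = 660; 48 × (1 + 12/2) = 336; ratio 1.96
- α/β = 3: 60 × (1 + 20/3) = 460; 48 × (1 + 12/3) = 240; ratio 1.92
- α/β = 5: 60 × (1 + 20/5) = 300; 48 × (1 + 12/5) = 163.2; ratio 1.84
- α/β = 10: 60 × (1 + 20/10) = 180; 48 × (1 + 12/10) = 105.6; ratio 1.70

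These ratios compare what is prescribed to the target, not what reaches the airway.

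**The case against.** The strongest reply is that Appendix III is guidance. Section 6.2.6 leaves dose and fractionation to the treating physician, and the lung paragraph itself speaks of 3 to 5 treatments depending on location. A physician who sees a lesion beside an airway need not follow the default. This stands, and it limits the point to a difference in default assignment. A default that physicians are encouraged to follow should still be coherent.

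A second reply is that the list was never strictly paired. The intermedius is a right-sided entry with no left partner, and with the middle lobe entry it brings lesions near the right lower lobe bronchus into the central class when they lie within 2 cm of either. This also stands and makes the right-sided gap smaller. It does not close it: the right middle lobe bronchus is named in addition to the intermedius, so the list does not let the intermedius stand for its branches, and no reason for the omission is given.

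A third reply is that section 3.2.8 is an eligibility rule that assigns no dose, so it does not contradict Appendix III outright. That is fair. The trachea point is that one section admits a kind of lesion for which the other makes no explicit provision.

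A reader might also infer that the airway itself receives about 1.9 times the biological dose. The documents do not support that. In the 3-fraction table the bronchus limit corresponds, at an assumed α/β of 3, to 30 × (1 + 10/3) = 130 Gy. The 4-fraction table as printed has no bronchus row, and an airway at full prescription there would be at 240 Gy. On the printed limits, the non-central class is the one with an explicit bronchus cap.

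**Conclusion.** The point holds as a specific inconsistency with a bearing on safety and a limited reach. By default, a lung lesion within 2 cm of the right lower lobe bronchus only is placed at 20 Gy per fraction, and its left-sided counterpart at 12 Gy per fraction. The 30 Gy bronchus limit mitigates the right-sided case. Separately, a lung lesion abutting the trachea away from all listed airways defaults to non-central with no tracheal limit in the tables.

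This rests on reading the definition literally, on the physician following the encouraged default, and on the tables being complete as printed. The documents do not give the number of lesions affected, and it may be small.

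Three wider readings are not supported:
- That left and right lesions in general are handled differently: only those beyond 2 cm from every listed airway are, and the comparison of sides does not apply to the trachea.
- That section 3.2.8 marks abutting tumours as a toxicity exclusion: it excludes direct invasion only.
- That a planned analysis is distorted: section 11 plans subsets by primary cancer and no summary by central or non-central class.

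**What to change.** Reconcile section 3.2.8 with the Appendix III lung definition and constraint tables. The text should make explicit and consistent to which class a lung lesion near the right lower lobe bronchus belongs, and to which class one near or abutting the trachea belongs, or else give the reason for the asymmetry. It should also say whether the absence of a trachea row from both lung tables is intended. The sponsor's radiation oncologists decide the class and any limits; this review proposes neither.

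The cost is a short amendment to Appendix III, with no extra patients or procedures. The downside is possible re-planning of a few lesions.

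### Appendix III (lung): the constraint table for 4 fractions contradicts itself, with two chest wall maxima for any point, two skin rows with different limits, and rows that imply 5 fractions

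*Combined protocol and SAP*

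**What the plan says.** Appendix III (LUNG) gives two schedules. For central tumors, defined by distance from the carina and named bronchi, "SRS dose will be 48 Gy in 4 fractions". For all others, "For non-central lesions, SBRT dose will be 60 Gy in 3 fractions". Each schedule has its own table of organ limits.

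The table headed "Dose constraints for 48 Gy in 4 fractions" has three columns after the organ name: Volume, Volume Max and Max Point Dose. The cord, skin and lung rows put a volume in cc in the first of these. The chest wall row puts *Any point* there, followed by 32 Gy (8 Gy/fx) and 40 Gy (10 Gy/fx). Skin has two rows.

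The table headed "Dose constraints for 60 Gy in 3 fractions" has a single limit per organ, at any point. For the chest wall it is "24 Gy (8 Gy per fx".

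Section 6.2.5 defines the target: "Planning treatment volume (PTV) will be GTV with margin appropriate for set-up error and movement". Section 6.2.6 sets the standing of the appendix: "the exact fractionation and dose is at the discretion of the treating physician", and "encouragement is made to adhere to the guidelines outlined in Appendix III".

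**The concern.** A limit on a volume and a limit on a point are different quantities, and a table may give both for one organ. That works only if the first names its volume. In the chest wall row it does not, so both figures attach to any point and the row gives two answers. Two other features of the table also give two answers: a second skin row for the same volume, and totals that do not agree with the per-fraction doses beside them under a 4-fraction heading.

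The table exists to protect normal tissue, and acceptable toxicity is a primary endpoint (sections 2.0 and 11.0). If planners resolve the ambiguity differently, patients on the same nominal schedule are planned to different limits, and the toxicity result mixes them. Local control of metastatic sites, a secondary endpoint, could also be affected if one planner gives up target coverage to meet a limit and another does not.

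**Working it through.** All dose figures are from Appendix III (LUNG). The target definition is from section 6.2.5.

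**1. Do the chest wall figures belong to their tables?** Total dose ÷ dose per fraction gives the implied number of fractions.
- 4-fraction table: 32/8 = 4 and 40/10 = 4.
- 3-fraction table: 24/8 = 3.

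All three fit their headings, and the 4-fraction row has the same four cells as the cord and skin rows. Nothing in the text points to a shifted cell.

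**2. What does the 4-fraction chest wall row require?** Let D be the dose at a point in the chest wall.
- Literal reading: D ≤ 32 Gy and D ≤ 40 Gy both apply to any point. At D = 36 Gy the plan is 36 − 32 = 4 Gy over one limit and 40 − 36 = 4 Gy under the other. The conflict spans 40 − 32 = 8 Gy.
- If 32 Gy is instead a volume limit, its volume is missing and compliance cannot be judged.

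**3. Do the other rows of that table fit its heading?**

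| Row | Volume | Limit | Total (Gy) | Per fraction (Gy) | Implied fractions | 4 × per fraction (Gy) |
|---|---|---|---|---|---|---|
| Cord | <0.25 cc | volume | 22.5 | 4.5 | 5 | 18 |
| Cord | – | point | 30 | 6 | 5 | 24 |
| Skin, first row | <10 cc | volume | 30 | 6 | 5 | 24 |
| Skin, first row | – | point | 32 | 6.4 | 5 | 25.6 |
| Lung | 1500 cc | volume | 12.5 | 2.5 | 5 | 10 |
| Skin, second row | <10 cc | volume | 33.2 | 8.3 | 4 | 33.2 |
| Skin, second row | – | point | 36 | 9 | 4 | 36 |

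Five of these seven limits imply 5 fractions. For those five, the printed total exceeds four times the printed per-fraction dose by a factor of 5/4 = 1.25 (for example 22.5/18). The appendix allows 3 to 5 treatments for lung but states no 5-fraction lung prescription to which these rows could belong.

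**4. How far apart are the skin rows?** For the same volume, 33.2 − 30 = 3.2 Gy. For the point maximum, 36 − 32 = 4 Gy. A skin point at 34 Gy fails the first row and passes the second.

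**5. The 3-fraction schedule.** The chest wall limit is 24/60 = 40% of the prescription. The full set of limits in that table is cord 18/60 = 30%, esophagus 27/60 = 45%, heart 30/60 = 50%, bronchus 30/60 = 50%, skin 40% and chest wall 40%. Every organ limit lies below the target dose, as expected when the organ is outside the target. The chest wall limit and the prescription meet in the same tissue only if the target plus its margin extends into chest wall. No section says what applies then.

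**The case against.** **The two chest wall figures sit in different columns.** 32 Gy is under Volume Max and only 40 Gy is under Max Point Dose, so this could be a missing volume rather than two point maxima. That is a fair alternative, and a cell misread from the PDF cannot be excluded. Neither rescues the row as printed: one reading gives two maxima, the other a limit that cannot be evaluated. It might also be said that the lower figure simply governs, but then the 40 Gy cell does nothing, which itself calls for correction.

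**Appendix III is a guideline.** Section 6.2.6 leaves dose and fractionation to the physician and only encourages adherence. This weakens any claim that departures are protocol deviations. It does not say which of two printed limits a physician who wishes to adhere should use, and its wording covers dose and fractionation rather than organ limits.

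**The 4-fraction table serves central tumors,** so its chest wall row may seldom be decisive. That is plausible, though the documents give no frequency. The cord, lung and skin rows of the same table do not depend on the target being near the chest wall.

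**Stronger readings that the documents do not support.** A reader might infer that 60 Gy to non-central lesions contradicts a 24 Gy chest wall limit in general. It does not: one is a target dose and the other an organ limit, and by that logic every row of the table would be a contradiction. Nor do the 24 Gy and 32 Gy limits conflict: both are 8 Gy per fraction, for different schedules. Comparing the tables by biologically effective dose would need an alpha/beta ratio that the documents do not give. Nothing shows that all lesions near the chest wall are affected, or that deviations would be routine.

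**Conclusion.** The 4-fraction lung table is wrong as printed and should be corrected. The chest wall row leaves an 8 Gy band (32 to 40 Gy) in which a point both passes and fails. Skin has two sets of limits 3.2 and 4 Gy apart. Five limits in the cord, first skin and lung rows carry totals 25% above four times their per-fraction doses. This rests on the table as read from the PDF; the arithmetic supports that reading for the chest wall row but does not prove the layout.

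The 3-fraction chest wall limit is a secondary matter: a gap for targets that overlap chest wall, softened by physician discretion, and not a general contradiction. The effect on toxicity or local control cannot be sized, because the documents give neither the number of lung lesions on each schedule nor the share whose planning volume reaches chest wall. No view is taken here on which limit, schedule or dose is right.

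**What to change.** 1. Compare the 4-fraction lung table with the sponsor's source file to rule out a layout fault.
2. Reconcile that table so that each organ has one row, each volume limit names its volume, each organ has at most one point maximum, and totals, per-fraction doses and heading agree.
3. Reconcile the 3-fraction chest wall limit with the prescription for targets whose planning volume overlaps chest wall, and state in Appendix III what applies in that case.

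The sponsor sets all values and rules. The cost is edits to one table and one added sentence in an amendment, with no new procedures, visits or patients.

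### Appendix III's 4-fraction organ dose limits are internally inconsistent for lung and liver and should be confirmed and reissued

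*Combined protocol and SAP*

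**What the plan says.** Everything here is in Appendix III unless another section is named.

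- **Lung.** The lung text states that "SBRT to lung lesions will consist of 3-5 treatments depending on location of tumor". For central tumors the "SRS dose will be 48 Gy in 4 fractions"; non-central lesions get 60 Gy in 3 fractions. No 5-fraction lung dose is given. The table headed "Dose constraints for 48 Gy in 4 fractions" gives a total and a per-fraction dose for each limit, and it has two skin rows for the same <10 cc volume.
- **Liver.** The regimens are 60 Gy in 3 or in 4 fractions, with 4 preferred. The text sets liver, kidney, cord and stomach limits for 3 and for 5 fractions. The table beneath it has columns for 3 and for 4 fractions.
- **Adrenal.** The dose is 50 Gy in 5 fractions, and the limits are headed "Maximum Dose in 5 Fractions".
- **Status.** Section 6.2.6 leaves exact dose and fractionation to the treating physician and encourages use of Appendix III. Sections 2.0 and 11.0 make acceptable toxicity (grade 3 or less) a primary endpoint.

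**The concern.** A total limit and a per-fraction limit printed side by side should agree once multiplied by the number of fractions in the heading. In the 4-fraction lung table most do not, so a planner cannot tell which figure was meant. Skin has two competing rows, and the cord limit depends on which site's table is consulted. In the liver section, the preferred regimen's limits carry one fraction number in the text and another in the table.

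These are the stated normal-tissue limits for central lung tumors and for the preferred liver regimen, in a trial with a toxicity primary endpoint. Two careful planners could hold the same central-lung case to different cord or skin limits. One patient may also have lung and liver lesions treated together, as the example schedule in section 6.2.6 shows.

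**Working it through.** **1. Lung table, 4 fractions.** Implied fractions = total ÷ per-fraction dose. Total ÷ 4 is the dose per fraction if the total is kept; 4 × per-fraction dose is the total if that dose is kept.

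| Entry | Total (Gy) | Gy/fx | Implied fractions | Total ÷ 4 | 4 × Gy/fx |
|---|---|---|---|---|---|
| Cord, <0.25 cc | 22.5 | 4.5 | 5 | 5.625 | 18 |
| Cord, point | 30 | 6 | 5 | 7.5 | 24 |
| Skin row 1, <10 cc | 30 | 6 | 5 | 7.5 | 24 |
| Skin row 1, point | 32 | 6.4 | 5 | 8.0 | 25.6 |
| Lung, 1500 cc | 12.5 | 2.5 | 5 | 3.125 | 10 |
| Skin row 2, <10 cc | 33.2 | 8.3 | 4 | 8.3 | 33.2 |
| Skin row 2, point | 36 | 9 | 4 | 9 | 36 |
| Chest wall, volume column | 32 | 8 | 4 | 8 | 32 |
| Chest wall, point column | 40 | 10 | 4 | 10 | 40 |

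Five of nine give exactly 5 and four give exactly 4.

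*Control.* In the 60 Gy in 3 fractions table, 18/6, 27/9, 30/10, 30/10, 24/8 and 24/8 all give exactly 3. Exact whole-number ratios, beside a fully consistent table, are not what text-extraction damage would produce.

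*Skin.* The first row has the lower totals: 30/33.2 − 1 = −9.6% and 32/36 − 1 = −11.1%.

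**2. Liver text against liver table (Gy).**

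| Organ | Text, 3 fx | Text, 5 fx | Table, 4 fx | Gy/fx at 3 / 4 / 5 |
|---|---|---|---|---|
| Liver, 700 cm³ | 15 | 25 | 25 | 5 / 6.25 / 5 |
| Right kidney, 2/3 | 15 | 25 | 25 | 5 / 6.25 / 5 |
| Total kidney, 35% | 15 | 25 | 25 | 5 / 6.25 / 5 |
| Cord | 18 | 20 | 20 | 6 / 5 / 4 |
| Stomach | 30 | 35 | 35 | 10 / 8.75 / 7 |

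All five 4-fraction values equal the text's 5-fraction values. The adrenal table prints the same total-kidney, cord and stomach values (25, 20 and 35 Gy) for 5 fractions.

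**3. Cord limit across sites.** At 4 fractions the lung table gives 30 Gy and the liver table 20 Gy: 30/20 − 1 = 50%. The 3- and 5-fraction cord point limits are 18 Gy in 3 (lung table, liver text) and 20 Gy in 5 (liver text). The adrenal table also gives 20 Gy in 5. The liver and adrenal cord rows do not themselves say point dose; for liver, that reading comes from the text.

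**4. Why 4/5 scaling cannot set the final limits.** Applied to the liver text's 5-fraction limits, it gives cord 4 × 4 = 16 Gy and stomach 4 × 7 = 28 Gy. Both fall below the 3-fraction limits of 18 and 30 Gy.

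**The case against.** The strongest reply is that Appendix III is a set of guidelines and section 6.2.6 gives the physician discretion. A lung planner who honors both figures simply ends up with the stricter one, and nothing shows that any plan was affected. This softens the point and argues against the highest severity. It does not remove it: discretion over dose and fractionation does not say which of two conflicting organ limits was intended, and the liver text words its limits as prohibitions.

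Several stronger readings are tempting but unsupported:

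- **The printed totals allow a 25% overdose.** Total ÷ 4 exceeds the per-fraction figure by 25% (5/4 − 1) in the five mismatched entries. That measures the contradiction, not an excess dose, because either figure or the heading could be the slip. For skin, the row that implies 5 fractions has the lower totals.
- **Liver planners face two rival 4-fraction limits.** They do not. The table gives one 4-fraction set and the text gives none. The defect is a text/table mismatch, and the text's 5 could be the slip, although the adrenal table points the other way.
- **The liver and kidney limits are 67% too high.** That figure (25/15 − 1) assumes the true 4-fraction limit equals the 3-fraction one, which nothing in the documents supports. It is a bound, and zero error is equally possible.
- **Chest wall is contradictory too.** The 32 and 40 Gy values sit under different column headings and both fit 4 fractions. The any-point label may be a misplaced volume entry.
- **The 30 and 20 Gy cord figures are independent 4-fraction standards.** The 20 Gy comes from the column whose label is in doubt. The lung table also has a cord volume limit, which the liver table lacks. The gap is real only as printed.

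**Conclusion.** The 4-fraction limits are internally inconsistent. Five of nine lung pairs do not fit the heading, skin <10 cc has two sets of limits, all five liver values match the text's 5-fraction limits, and the printed cord limit differs by 10 Gy between sites. The arithmetic needs no outside assumption beyond equal fractions.

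The documents do not show which figures are wrong, or in which direction. They give no tissue-tolerance data, so harm is not quantified. A 5-fraction lung set may have been merged into the table, since the text mentions up to 5 treatments, but this is conjecture. A reader might infer that the toxicity endpoint is compromised. The documents do not support that: dose is already discretionary and primary treatment varies by patient. Sample size and analysis are unaffected. This should be fixed on patient-safety grounds.

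**What to change.** Radiation oncology and physics should confirm and reissue:

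1. the 4-fraction lung table, with every total equal to 4 × its per-fraction dose and a single skin row;
2. a liver text and column that name the same number of fractions, with confirmed 4-fraction values;
3. one confirmed 4-fraction cord point limit for both sites.

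At the same time, check whether the chest-wall any-point cell is a misplaced volume entry. Do not set final limits by 4/5 scaling.

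**Until reissue**, 4-fraction lung plans should meet both the printed total and the printed per-fraction figure in every row, skin included. Over 4 equal fractions this means cord 18 Gy to <0.25 cc and 24 Gy point, skin 24 Gy (<10 cc) and 25.6 Gy (point), and lung 10 Gy. Where achievable, keep the cord point dose to 20 Gy, the lower printed 4-fraction value. These are holding rules, chosen because they breach no printed lung figure; they are not proposed as final limits. No interim numbers are offered for liver, kidney, stomach or chest wall, because the documents give no basis for them.

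Record which limits were used for plans already made.

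**Cost.** A short protocol clarification and a look-back at 48 Gy/4 lung and 60 Gy/4 liver plans. In the interim, some central-lung plans may be harder to meet or lose target coverage: 20 Gy is 33% below the printed 30 Gy cord limit and 17% below 24 Gy. No added patients and no change to the analysis.
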